8.2.8.2. Diarrhoea management

Considering the GLP toxicity studies and the preliminary clinical data with S64315 (17/38, 44.7%) patients treated in the S64315 monotherapy AML and MDS study experienced diarrhoea, diarrhoea should be closely monitored.

The patient should be instructed to contact the physician/other study personnel in case of severe diarrhoea.

In case of diarrhoea, management and treatment approaches should be implemented according to routine practice and applicable guidelines. In case no guideline is available, investigators should refer to ESMO clinical practice guidelines for diarrhoea in adult cancer patients.

Guidance for diarrhoea management (ESMO, 2018) is summarised in [Appendix 7](#).

8.2.9. Tumour Lysis Syndrome management

Tumour Lysis Syndrome (TLS) prophylaxis is required during the administration of S64315 in combination with azacitidine for patients with active disease, in case of intra-patient dose escalation to a new assigned dose(s) and in case of readministration after one or both IMPs interruption \geq 28 days.

Even if only patients with low/intermediate risk of TLS are included, TLS prophylaxis for intermediary risk should be implemented for any patient considering the expected overlapping toxicity of the combination. TLS management will be based on institutional guidelines and published criteria ([Cairo, 2010](#)) and on the recommendations described below.

Hydration

Adequate hydration should be ensured for all patients according to routine clinical practice and international guidelines (Cairo, 2010).

In order to prevent the risk of TLS, hydration will be made mandatory during the LID period and during the two first infusions of S64315 at the full tested dose (LID1, LID2, C1D2 and C1D9). Patients should be encouraged to drink up to 1.5 to 2.0 L of water daily starting the day before the S64315 infusion, and 24 hours after. Intravenous fluids at 50cc/hour or higher are recommended to be administered for at least 12 hours prior to the S64315 infusion, then IV fluid should be continued according to the investigator's judgement. The rate of IV fluids should be adjusted per clinical judgment.

Anti-hyperuricaemic agents

Allopurinol is recommended for patients with active disease throughout the study. Patients who develop laboratory TLS should receive rasburicase unless clinically contraindicated (Cairo, 2010).

Laboratory assessments (see section 8.2.2).

Before and following S64315 infusions during the LID period (LID1 on D-13 and LID2 on D-6):

WBC, serum uric acid, serum calcium, serum phosphorus, serum potassium, serum creatinine and LDH must be monitored at the following time points:

- Prior to S64315 administration (LID1 and LID2 predose)
- 2h, 4h and 8h after S64315 EoI (LID1 and LID2)
- 24h (\pm 2h) after S64315 EoI (LID1 and LID2)

Before and following the first azacitidine administration (C1D1) and first S64315 infusion (C1D2) of cycle 1:

WBC, serum uric acid, serum calcium, serum phosphorus, serum potassium, serum creatinine and LDH must be monitored at the following time points:

- Prior to azacitidine first injection (C1D1 predose)
- 1h30 and 6h after azacitidine first injection (C1D1)
- After azacitidine second injection and prior to first S64315 infusion (C1D2)
- 2h, 4h and 8h after S64315 EoI (i.e. C1D2)
- 24h (\pm 2h) after S64315 EoI (i.e. C1D3)

Beyond the first infusion of S64315 (applicable for all patients with a risk of developing TLS according to the investigator's judgment):

WBC, serum uric acid, serum calcium, serum phosphorus, serum potassium, serum creatinine and LDH must be monitored at the following time points:

- Prior to each S64315 infusion (i.e. CxD9, CxD16, CxD23 predose)
- 2h, 4h and 8h after each S64315 EoI (i.e. CxD9, CxD16, CxD23)
- 24h (\pm 2h) after each S64315 EoI (i.e. CxD10, CxD17, CxD24)

Electrolyte abnormalities should be corrected promptly.

Hospitalization

To enable close in-patient TLS monitoring and management, patients must be hospitalized:

- at least 12h before the day of LID1 and for at least 24h after LID1
- at least 12h before the day of LID2 and for at least 24h after LID2

- at least 12h before C1D1 and for at least 24h after C1D2 S64315 infusion (including C1D1, C1D2 and C1D3)

If a biological or clinical TLS develops, additional measures should be implemented according to guidelines (Howard, 2011), including dialysis if clinically indicated.

In case of intra-patient dose escalation, the patient will be hospitalized for at least 3 days.

8.2.10. Infusion Related Reaction management

As the risk of Infusion Related Reaction (IRR) is not yet well characterized, it is challenging at this stage to propose a standardized prophylactic treatment before the first S64315 infusions. However, before S64315 infusion during LID period, cycle 1, and during following cycles at the investigator's discretion according to conventional practices, patients should receive the following:

- Hydration: already planned in the frame of TLS prophylaxis (see section 8.2.9)
- Corticoids (dexamethasone): already planned in the frame of nausea/vomiting prevention (see section 8.2.8.1)
- Additionally, according to investigator's opinion, anti H1 and/or anti H2 could be administered before S64315 infusion
- Patient's risk factors to develop IRR such as age-related factors, concomitant diseases (e.g. chronic respiratory diseases, cardiovascular diseases, severe atopic disease) and concomitant medications (e.g. β -adrenergic blockers and angiotensin-converting enzyme inhibitors), should be assessed before treating the patient

In addition, patient vital signs (BP, HR, temperature) should be monitored as follows:

- during the LID period for each S64315 infusion: EoI, at least 2h and 24h after EoI (LID1 and LID2)
- during Cycle 1 for each S64315 infusion: EoI and at least 2h after EoI (C1D2, C1D9, C1D16, C1D23)

In case of occurrence, IRR management will be performed according to ESMO guidelines (ESMO, 2017) as presented in Figure (8.2.10) 1 or according to local practice guidelines. If the patient experiences an IRR of grade 1 or 2, the infusion rate should be immediately decreased by 50% of the initial rate without exceeding 3 hours of total infusion time or infusion immediately stopped according to the investigator judgment and based on the severity of symptoms. The patient's vital signs (eg: blood pressure, heart rate, respiration, temperature) should be monitored every 15 minutes until the event has resolved.

[figure not shown]
To allow better characterization of IRR, it is recommended to perform blood samplings for the measurement of tryptase levels optimally 15 min to 3h after the onset of the IRR. A new sample should be obtained from 48h to 72h after the onset of the event (baseline value).

With regards to rechallenge, the following guidelines should be considered:

- Grade 1 IRR: adequate prophylaxis should be implemented before each subsequent S64315 infusion
- Grade 2 IRR: adequate prophylaxis should be implemented before each subsequent S64315 infusion

- Grade 3 IRR:
 - If serious adverse event: no rechallenge is permitted
 - If non-serious adverse event: rechallenge is permitted according to the expected benefit risk ratio and provided that an adequate prophylaxis is implemented before each subsequent S64315 infusion, and upon sponsor's approval
- Grade 4 IRR: rechallenge is not permitted.

Figure (8.2.10) 1 - Management of IRR to systemic anticancer therapy ESMO clinical practice guidelines

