4.1.3.6. DLT management

Study treatments must be delayed for any patient who experienced a DLT. Conditions to resume treatment are described in [section 8.12](#).

All DLT will be reported to I.R.I.S. within 24h via the DLT form in the electronic Case Report Form (eCRF). The eCRF ‘Adverse Event’ page should then be filled in, without waiting for the results of the clinical outcome or of additional investigations. When data of the DLT form are submitted, an e-mail will be immediately and automatically sent to the sponsor.

If the eCRF is unavailable when the investigator is informed of the DLT, he/she should:

- report the DLT on a paper ‘DLT form’
- send the form by fax immediately to I.R.I.S. at the following number: [contact]

As soon as the eCRF becomes available again, the investigator must enter the data in the eCRF.

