8.8. Classification of an adverse event (seriousness, severity, causality, expectedness)

It is important that the investigator gives his/her own opinion regarding the **seriousness**, the **intensity** of the event as well as the **cause-effect relationship** between an adverse event and the IMPs. This evaluation must be assessed by the investigator and reported in the AE form. In addition, the sponsor will be responsible for the evaluation the **expectedness** of the event (see [section 8.10](#)).

The Seriousness should be evaluated according to international guidance (see definition in [section 8.4](#), in accordance with ICH Topic E2A and DIRECTIVE 2001/20/EC OF THE EUROPEAN PARLIAMENT AND OF THE COUNCIL of 4 April).

The severity of all AEs will be graded according to the National Cancer Institute Common Toxicity Criteria for Adverse Event (NCI CTCAE) on a five-point scale (Grade 1 to 5):

- Grade 1: Mild; asymptomatic or mild symptoms; clinical or diagnostic observations only; intervention not indicated
- Grade 2: Moderate; minimal, local or non-invasive intervention indicated; limiting age-appropriate instrumental ADL¹

¹ Instrumental Activities of Daily Living (ADL) refer to preparing meals, shopping for groceries or clothes, using the telephone, managing money, etc.

- Grade 3: Severe or medically significant but not immediately life-threatening; hospitalization or prolongation of hospitalization indicated; disabling; limiting self-care ADL²
- Grade 4: Life-threatening consequences; urgent intervention indicated
- Grade 5: Death related to AE

The causal relationship to the IMPs, to the experimental procedures or to disease progression must be assessed when reporting the AE in the AE form. Cases ticked 'related' by the investigator or judged by the sponsor as having a reasonable suspected causal relationship to the IMPs (AE linked to the mechanism of action of the test drug, etc.), will be considered as suspected Adverse Drug Reaction. In general, if a relationship between AE and drug is at least reasonably possible (i.e. the relationship cannot be ruled out) it is to be considered as 'related'.

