Grade 3	Omit dose until resolved to Grade ≤ 1, and increase ophthalmic monitoring frequency to at least once a week, and refer the patient to an ophthalmologist within one week for further evaluation, then: 
 - If resolved in ≤ 14 days, ↓ 1 dose level - If resolved in > 14 days, discontinue patient from test drug treatment
Grade 4	Discontinue test drug treatment and refer the patient to an ophthalmologist for monitoring
Haematological abnormalities (myelosuppression)	
Neutropenia and thrombocytopenia Grade 4	If bone marrow clearance, omit dose and/or interrupt azacitidine until count recovery: 
 - If resolved in < 28 days, then maintain the dose level - If resolved in > 28 days, then consider discontinuing patients from study unless the patient has evidence of clinical benefit and in discussion with the Sponsor a decision is made to continue therapy at a lower dose
Other AEs	
Grade 3	If Grade 3 (except those correctable within 7 days and deemed by the investigator to be not clinically important), hold treatment until resolved to Grade ≤ 1 or baseline, then: 
 - If resolved in ≤ 14 days, ↓ 1 dose level - If resolved in > 14 days, discontinue patient from test drug treatment
Grade 4	Discontinue test drug treatment
NOTE In some particular cases, a patient with a Grade 3 or Grade 4 AE may resume treatment at the lower dose level if in the opinion of the Investigator and after discussion with the Sponsor, the event is not life-threatening, and the patient can be managed and monitored for recurrence of the AE. In case of TLS Grade 3 or 4, the dose adaptation of the study drugs will be discussed between the sponsor and the investigator according to the patient's benefit/risk assessment.	

All dose modifications should be based on the worst preceding toxicity.

Patients may receive supportive care (e.g. packed red blood cells) as per local institutional guidelines.

^a Common Toxicity Criteria for Adverse Events (CTCAE v5.0)

^b If Grade 3 or 4 hyper-bilirubinaemia is due to the indirect (non-conjugated) component only, and haemolysis as the aetiology has been ruled out as per institutional guidelines (e.g. review of peripheral blood smear and haptoglobin determination), then ↓ 1 dose level and continue treatment at the discretion of the investigator

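### For a serious Grade 3 infusion reaction that resolves within 14 days, section 8.2.10 bars rechallenge while the 'Other AEs' row of Table (8.12) 1 restarts S64315 one level lower, with no stated precedence.

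*Protocol*

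**What the plan says.** Section 8.2.10 gives rechallenge rules by grade, introduced with "With regards to rechallenge, the following guidelines should be considered".

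- Grade 3, serious: "If serious adverse event: no rechallenge is permitted".
- Grade 3, non-serious: "If non-serious adverse event: rechallenge is permitted according to the expected benefit risk ratio and provided that an adequate prophylaxis is implemented", and with the sponsor's approval. Dose level is not mentioned.
- Grade 4: "Grade 4 IRR: rechallenge is not permitted".

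Table (8.12) 1 sets interruption and re-initiation of S64315 by type of toxicity. It has no row for infusion reactions and does not cite 8.2.10. Its residual 'Other AEs' row holds a Grade 3 event until Grade 1 or lower, or baseline. Then "If resolved in ≤ 14 days, ↓ 1 dose level"; if recovery takes longer than 14 days, S64315 is discontinued. Grade 4 is discontinued. A NOTE below adds that in particular cases a patient with a Grade 3 or 4 event "may resume treatment at the lower dose level", after discussion with the sponsor and provided that the event is not life-threatening.

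Two other places route the reader. Section 4.1.3.6, on patients with a DLT, says "Conditions to resume treatment are described in" section 8.12. Section 6.1.1 refers all toxicity-driven dose adaptations to section 8.12. Neither mentions 8.2.10.

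**The concern.** A drug-related Grade 3 infusion reaction meets the DLT catch-all in Table (4.1.3.5) 1, which covers any Grade 3 or higher event. A site that treats it as a DLT goes from 4.1.3.6 to 8.12 and arrives at a rule that allows a restart. A site that treats it as an infusion reaction goes to 8.2.10 and, if the event is serious, arrives at a rule that does not.

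Whether a patient is re-infused after a serious reaction is a safety matter, and it should not depend on the section opened first. The data are affected too. Dose interruptions, reductions and dose intensity are among the endpoints for the primary objective (protocol Table (3.4) 1; SAP section 1.2). The SAP also tabulates the action taken on study drug (section 3.4.2). It has a deviation category for patients who met withdrawal criteria but were not withdrawn (section 4.2.1.2). The same re-infused patient could look compliant under 8.12 and non-compliant under 8.2.10.

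**Working it through.** No arithmetic applies. The check sets the two rules side by side for each case.

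| Infusion reaction | Section 8.2.10 | Table (8.12) 1, 'Other AEs' | Compatible? |
|---|---|---|---|
| Grade 3, serious, resolved in 14 days or less | No rechallenge | Restart one dose level lower | No |
| Grade 3, serious, resolved in more than 14 days | No rechallenge | Discontinue | Yes, by default |
| Grade 3, non-serious, resolved in 14 days or less | Rechallenge with prophylaxis and sponsor approval; dose not mentioned | Restart one dose level lower; prophylaxis and approval not mentioned | Both can be met, but the conditions differ |
| Grade 4 | No rechallenge | Discontinue | Yes, by default |

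**First row.** The table row does not separate serious from non-serious events, so a serious Grade 3 reaction fits it. The instructions are opposite. Recovery within 14 days is plausible for an acute infusion event: 8.2.10 asks for vital signs every 15 minutes until resolution and a baseline tryptase sample 48 to 72 hours after onset.

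**Second row.** The defaults agree. Only the NOTE, used at discretion after sponsor discussion, could lead elsewhere.

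**Third row.** A site could obtain approval, give prophylaxis and reduce the dose, and so satisfy both passages. A site reading only 8.2.10 has no instruction to reduce. A site reading only the table has no instruction to seek approval or give prophylaxis. The table row also leaves out events correctable within 7 days that the investigator considers not clinically important; 8.2.10 has no such exception.

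**Fourth row.** The NOTE requires an event that is not life-threatening. Section 8.8 describes Grade 4 by life-threatening consequences, so a Grade 4 reaction so defined does not meet the exception.

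**Effect on the DLT count.** The reaction is itself the DLT, whichever section then governs re-treatment. Under Table (4.1.3.5) 2, stopping because of a DLT does not make a patient non-evaluable. The DLT input to the Bayesian logistic regression model (BLRM) is therefore the same either way.

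**The case against.** The strongest reply is that the specific rule governs. Table (8) 1 assigns infusion reactions to section 8.2.10, which has its own grade-by-grade rules, while 'Other AEs' is a residual row in a table of recommended modifications. The cardiac and hepatic sections refer to 8.12 for treatment consequences, and 8.2.10 does not. This reading is plausible, but the protocol never states it. The 8.2.10 rules are introduced as guidelines to be considered, which weakens any claim that they override a table to which 4.1.3.6 and 6.1.1 point without exception. Of the five risks in Table (8) 1, cardiac, hepatic and gastrointestinal toxicity have rows in Table (8.12) 1 and tumour lysis is named in its NOTE. Only infusion reactions are absent, and nothing says that the absence is deliberate.

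The scope is also narrow, and that stands. The table's instructions are headed as applying during a cycle, so they do not plainly cover the two lead-in infusions, which have their own postponement and withdrawal criteria in section 5.8.1.

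Serious events and DLTs must be notified within 24 hours, and S64315 infusions are at least 5 days apart, so the sponsor should know before the next dose. That reduces the practical risk, but it does not tell the sponsor or the site which rule holds.

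Two stronger readings are tempting. A reader might infer that the table lets some Grade 4 reactions resume; its default and the NOTE's condition do not support that. A reader might also infer that most Grade 3 reactions are serious, because section 8.8 includes "hospitalization or prolongation of hospitalization indicated" in its description of Grade 3. That description lists alternatives, 8.2.10 expressly provides for non-serious Grade 3 reactions, and patients are already in hospital by protocol around the lead-in doses and the start of Cycle 1. The documents do not show which branch is usual.

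**Conclusion.** The protocol is inconsistent as written for one case: a serious Grade 3 infusion reaction that resolves within 14 days. The conflict rests on placing the reaction under 'Other AEs', the only row that can hold it and the one reached through the routing text. For a non-serious Grade 3 reaction the passages are incomplete with respect to each other rather than contradictory. Grade 4 does not belong to the point.

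The documents give no infusion-reaction rate, so the number of patients affected cannot be stated. Any effect is on later exposure, on interruption, reduction and discontinuation summaries, and on deviation status, all of which are descriptive. The SAP says that escalation was stopped and that the expansion will not be conducted. This limits future exposure but leaves open how a re-infused patient should be classified. The matter is worth correcting because it concerns re-treatment after a serious reaction and the remedy is small.

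**What to change.** Reconcile section 8.2.10 with Table (8.12) 1 so that one agreed rule applies to serious Grade 3 and one to non-serious Grade 3 infusion reactions. This can be done with an infusion-reaction row in the table, or with a cross-reference between the two sections and a statement of which takes precedence. For non-serious Grade 3, the agreed text should state together whether sponsor approval, prophylaxis and a dose reduction are required. Make sections 4.1.3.6 and 6.1.1 point to the same place. Which clinical rule applies is for the sponsor's clinicians to decide.

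For the report, state which rule was used when classifying any affected patient as a protocol deviation. The cost is protocol wording only; sample size, the dose-escalation model and data collection do not change.

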8.2.11. Specific COVID-19 situation

In case of highly suspected COVID-19 infection (based on typical symptoms or typical chest CT scan images) or confirmed COVID-19 infection (based on positive COVID-19 biological testing), the study treatment(s) should be immediately interrupted.

The study treatment(s) could be restarted if patient is asymptomatic for at least 15 days after the diagnosis or with a negative test.

8.3. Definition of adverse events

An adverse event is defined as any untoward medical occurrence in a patient participating in a clinical study, whether or not there is a causal relationship with the IMPs and/or experimental procedures, occurring or detected from the date the patient signs the information and consent form, irrespective of the period of the study.

An adverse event can therefore be:

- any unfavourable and unintended sign (including an abnormal finding from an additional examination such as lab tests, X-rays, ECG, etc.) which is deemed clinically relevant by the investigator
- any symptom or disease
- any worsening during the study of a symptom or a disease already present when the patient entered the study (increase in frequency and/or intensity), including the studied pathology
- and detected during a study visit or at an additional examination or occurred since the previous study visit (including relevant event reported in patient's diary or safety evaluation scale)

Of note:

- Any **hospitalisation for administration of anti-tumour treatment and/or associated protocol (during or after the study) or other care measures for cancer (e.g. overnight hospital stay to receive a blood or platelets transfusion), for social reasons, educational purpose** (e.g. learning of diabetes management by the patient) or routine check-up should not be considered as an adverse event and should not be reported in the eCRF.
- The following procedures, whether planned before the study or not, whether leading to a hospitalisation or not, **should not be reported in the eCRF and kept in the source data (or patient file)**:
 - therapeutic procedures related to a non-aggravated medical history (e.g. cataract extraction not due to an aggravation of the cataract during the study, haemodialysis sessions related to a renal insufficiency not aggravated during the study)
 - prophylactic procedures (e.g. sterilisation, wisdom teeth removal)
 - comfort procedures (e.g. cosmetic surgery)
 - control procedures of a pre-existing condition without aggravation (e.g. colonoscopy to control the remission of colon cancer)

8.4. Definition of Serious adverse events

A Serious Adverse Event (SAE) is any adverse event that, at any dose:

- results in death
- is life-threatening⁽¹⁾
- requires inpatient hospitalization or prolongation of existing hospitalization
- is medically significant⁽²⁾
- results in persistent or significant disability/incapacity⁽³⁾
- is a congenital anomaly/birth defect⁽⁴⁾

⁽¹⁾ Life-threatening in this context refers to an event in which the patient was at risk of death at the time of the event; it does not refer to an event which hypothetically might have caused death if it were more severe.

⁽²⁾ Any event that might not be immediately life-threatening or result in death or hospitalisation but might jeopardise the patient or might require intervention to prevent one of these outcomes (for example: oedema or allergic bronchospasm that required intensive treatment at home, blood dyscrasia, convulsions that do not result in hospitalisation, or development of drug dependence or drug abuse). The investigator should exercise his/her scientific and medical judgement to decide whether or not such an event requires expedited reporting to sponsor.

⁽³⁾ Disability/incapacity in this context refers to any event that seriously disrupts the ability of the patient to lead a normal life, in other words leads to a persistent or permanent significant change, deterioration, injury or perturbation of the patient's body functions or structure, physical activity and/or quality of life.

⁽⁴⁾ Congenital anomaly or birth defect refers to the exposure to the IMP before conception (in men or women) or during pregnancy that resulted in an adverse outcome in the child.

